6.2	SpinEchoFieldMap_AP	0:00:09	HCP
6.3	SpinEchoFieldMap_PA	0:00:09	HCP
	7. Diffusion-weighted im	lage	
7.1	dMRI dir98 AP	0:05:38	HCP
7.2	dMRI_dir98_PA	0:05:38	HCP
	8. Arterial spin labelin	g	
8.1	PCASLhr_SpinEchoFieldMap_AP	0:00:09	HCP
8.2	PCASLhr_SpinEchoFieldMap_PA	0:00:09	HCP
8.3	mbPCASL_PA	0:05:29	HCP
	9. Magnetic resonance spectrosco	opy (optional)	
9.1	svs_edit_859G_WS	0:08:40	Siemens
9.2	svs_edit_859G_NWS	0:00:14	Siemens
1	0. High-resolution hippocampus str	ucture (optional)
10.1	TSE HiResHp	0:03:31	HCP
Total time (excluding shimming and set-up)	1:05:25	

collected). This will require 8 tablespoons of blood to be drawn at 3 time points (baseline, 12 weeks, and 6-month follow up).

Imaging Biomarkers: Imaging data will be acquired from each subject **at baseline and at 12- weeks postrandomization** on a Siemens 3T Prisma system using a 32-channel head coil. Each scanning session will last 60 minutes and include 1) high-resolution T1- and T2 weighted structural scans (0.8 mm³ voxel size) using protocols developed for the Human Connectome Project (HCP) Lifespan Project (www.humanconnectome.org), which will be used for registration and to measure morphometric features as may be included as covariates and used for the detection and quantification of WMHs and CSF; and 2) three separate multiband EPI sequences with enhanced spatial (2 mm³) and temporal (TR: 720 ms) resolution and anterior-posterior/posterior-anterior (AP/PA) phase encoding to correct for anatomic distortions for the acquisition of rs- and task-related fMRI data used for the examination of working memory processing and functional connectivity. In addition, localizers and

field maps to correct for EPI anatomic distortions will be acquired. The morphometry sequences are optimized for determining brain tissue contrast with reduced distortion (van der Kouwe, Benner, Salat, & Fischl, 2008).

Functional Imaging: Analysis of rs-fMRI data will determine whether KK+KY leads to plasticity in brain network activity. To address our hypothesis that KK+KY versus MET will result in improved executive functioning (working memory) we will employ the N-back task. During resting periods and tasks, we will also assess physiological measures, including respiratory rate (respiration belt around the chest), GSR (electrodes on the hand), heart rate (pulse-ox), and end-tidal CO2 (nasal cannula).

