In the fitting method, f(i) is CBF at each individual delay and the final CBF is the mean of the estimated CBF per PLD. The 5 PLDs allow us to estimate CBF and ATT simultaneously using parameters fitting (2). Resulting rCBF and ATT maps will then be co-registered with the T1-weighted structural scan and normalized to the MNI standard space template with subsequent spatial smoothing.

WM Hyperintensities (WMH). The 3D T2-space images will be used to visualize WMHs by employing a semiautomated WMH identifier (Schwarz, Fletcher, DeCarli, & Carmichael). Briefly, WMH burden will be assessed based on the signal intensities of co-registered 3D MEMPR and T2-SPACE images, and population statistics on the spatial distribution and neighborhood structure of WM lesions. With every unit increase in WM burden, we will estimate % reduction in local brain tissue volume. GLM and multiple regression analyses will determine links between WM burden, clinical measures and vascular risk factors in each treatment group that may need to be controlled for.

Integration with Mood and Neurocognitive Measures. To test hypotheses about the relationships between imaging metrics and change in mood and cognition, we will derive domain summary scores for the 3 domains of interest – i.e., mood, memory, and executive functioning. Percent change in the mean Z scores will be calculated for each domain score and entered into analysis. We will first test the specific hypotheses described in the aims using separate GLMs for each MRI method. *Integration of Predictive Variables.* After analysis is complete on the predictive validity of each MRI measure, those that significantly predict remission/relapse or cognitive decline at follow-up will be combined for regression analysis. We will use the best single predictor in each modality. The final analysis will include a step-wise multiple regression analysis of clinical outcomes.

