Data will be analyzed using the SAS (v9.4) statistical package. Data will be examined initially to identify issues such as departures from normality, which might suggest the need for transformation (e.g., logarithmic). Demographic variables (e.g., age, gender, etc.) will be compared by treatment group and examined in relation to outcome variables; this would define one possible set of appropriate covariates, if needed. Correlations (a) among outcome measures and (b) among potential covariates will be examined to eliminate redundancy via possible data reduction, e.g., formation of composite scores or selection of single measures from sets of highly inter-correlated variables. Cognitive domain scores will be obtained as follows: for each neuropsychological test, raw scores will be converted to standardized (Z) scores with a mean of 0 and a SD of 1, based on all participants combined. Then, for each of the tests in a cognitive domain, the Z scores will be averaged to create a single Z score per cognitive domain.

The independent samples *t*-test or Chi-square test will be used to compare the demographic characteristics between the MET and KK+KY control group. The effect of intervention over time on the cognitive functions will be investigated in intention-to-treat (ITT) analyses. Measurements will be analyzed using linear mixed models; analyses will assume missing at random with missingness allowed. All models will include random intercepts to account for correlations between the repeated measures for each participant. The fixed components of the models will include effects of group and time and a group X time interaction, with post hoc analyses between times and groups. All statistical significance tests will be two-sided, and an alpha-level of 0.05 will be considered statistically significant for primary analyses and Bonferroni correction will be employed for post hoc analyses.

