Power analysis: The power analysis is focused on the primary aim of the study to assess whether the KK+KY and MET groups demonstrate comparable improvement in memory performance. We plan to enroll a total of 100 women in the study, anticipating an attrition rate of at most 10% based on our previous studies. Thus, we will most likely have a total of 90 completers. With a sample size of 45 per group, we achieve 80% power to detect equivalence within a margin of equivalence of 0.62, when the true difference between the means is assumed to be zero. In the PI's previous study using similar interventions on older adults with MCI, a between-group effect size of 0.3-0.4 was observed for the memory measures. In the proposed study, the target population is women with high risk for AD, hence we believe that the proposed sample size will have sufficient power to address the primary hypothesis of the study. With this sample size, we can also expect to detect an effect size of 0.60 at a significance level of 0.05 and 80% power for the secondary outcome measure (executive functioning). We intend to test the secondary outcomes adjusting for multiple comparisons using the Benjamini-Hochberg false discovery rate approach (which is more powerful than the simple Bonferroni correction). Further, we will report results of all proposed analyses and conclusions will be based on the pattern of results.

Data management: Data management and analysis support will be provided by the UCLA Semel Institute Statistical Core (SI-Stat) ([name]). The SI-Stat will provide needed software and technical support with a data manager operating under the supervision of [name]. The SI-Stat has a Dell PC computer network with

automated CD R/W backup and is set up for medium to large-scale data processing and analysis using available commercial database and statistical software. **1. Randomization.** Randomization schedules will be prepared in a masked manner by the statistician. **2. Data submission and quality control.** Data forms will be delivered from the originating location to the central data unit within one week of being generated. When errors, omissions, or unclear information is detected on the paper forms, a copy will be returned for corrections. The data manager will generate monthly reports summarizing missing and incorrect data will be sent to the PI.

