Each of these methods has significantly contributed to ongoing recruitment for other studies in our laboratory. [name] also has links to the local community of care providers for the elderly and to mental health professionals who could serve as a source of referrals. We anticipate having no competition with other studies for the same study population (i.e., those 50 years and older).

Recruitment. Participants will be recruited, assessed and randomized according to the scientific protocol and the consent procedures approved by the UCLA Institutional Review Board and the Office of Protection of Research Subjects. We project a recruitment period of two years to achieve recruitment of 100 participants. Our current rate of recruitment into antidepressant clinical trials for participants 55 years or older averages about 4-5 participants/month. We anticipate that the incentive to participate will be sufficient since participation includes free MET and KK-KY classes. Data analysis will be performed in year 2. We anticipate the dropout to be about 10% (45 completers per group) in the first 12 weeks, and additional 10% at 6 months and 12 months, leading to 35-36 completers per group at 12 months.

Table 6. Timeline.

Years of the project	Activities
Year 1,	Review assessment instruments; Inter-rater reliability sessions. Develop patient schedule with
	25

Years of the project	Activities
months 1-4	the UCLA CRC. Develop patient database with [name] and research assistants. Start subject recruitment at month 4.
Year 1, months 4-12	Continue recruitment (50 participants).
Year 2	Continue recruitment (50 participants). Conduct inter-rater reliability sessions.

Retention of participants. We have developed several successful strategies for retention of elderly participants. These include an ongoing and continuous process of consent to study procedures, involvement of family members whenever possible, and use of concerned and empathic clinicians and staff. However, it is important to note that our data analytic approach is robust to attrition.

Cohort maintenance. The comprehensive evaluation of participants prior to randomization and entry into the treatment trial is designed to minimize attrition. The evaluation of weekly compliance questionnaires will also alert the PI to potential attrition problems.

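### The imaging prediction model is selected and tested on the same women without validation, so its p-values are invalid and its R-squared is optimistic

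*Combined protocol and SAP*

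**What the plan says.** The protocol's paragraph Integration of Predictive Variables, within Integration with Mood and Neurocognitive Measures, sets out three selections in sequence.

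- Screen: of the MRI measures, "those that significantly predict remission/relapse or cognitive decline at follow-up will be combined for regression analysis".
- Reduction: "We will use the best single predictor in each modality".
- Final model: "The final analysis will include a step-wise multiple regression analysis of clinical outcomes".

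The paragraph gives no candidate list, screening threshold or stepwise entry rule. It describes no hold-out sample, cross-validation, permutation test or correction for optimism.

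Two general multiplicity rules exist elsewhere. Data analysis reserves Bonferroni for post hoc comparisons. Power analysis says: "We intend to test the secondary outcomes adjusting for multiple comparisons using the Benjamini-Hochberg false discovery rate approach". Neither is tied to this screen. For the microarray screen, by contrast, the protocol sets a 5% false discovery rate and a confirmatory RT-PCR step.

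On outcomes, the same section says "we will derive domain summary scores for the 3 domains of interest", namely mood, memory and executive functioning. Remission and relapse are not defined as outcomes anywhere in the trial.

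**The concern.** When predictors are chosen because they reach significance and the same data then supply the final test, the test no longer has its nominal error rate. The R-squared also reflects the luck of the selection. The plan attaches no correction or validation to this step. At stake is what may be said about imaging predictors of response: the protocol hopes its imaging programme will help delineate biomarkers that guide practice. A reader of the final model would see a small p-value and a non-trivial R-squared and could not tell either from noise. In addition, the screen as worded partly targets an outcome that this trial does not measure.

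**Working it through.** **Inputs from the protocol**

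- Sample: "Imaging data will be acquired from each subject" (Imaging Biomarkers). With 10% attrition, 100 × 0.90 = 90 women at week 12. For 12 months, Recruitment expects losses "leading to 35-36 completers per group at 12 months", about 71 in total.
- Threshold: "All statistical significance tests will be two-sided, and an alpha-level of 0.05 will be considered statistically significant for primary analyses" (Data analysis). I assume 0.05 two-sided for the screen and for forward stepwise entry, since neither is stated.
- Candidates: no count is given. A minimum list read from the imaging sections is structural regions 5 (hippocampus, ACC, amygdala, striatum, DLPFC), resting-state networks 5, N-back seeds 3, face-name seeds 3, DTI metrics 4 (FA, MD, AD, RD), ASL 2 (rCBF, ATT), and white matter hyperintensity burden 1. The total is 5 + 5 + 3 + 3 + 4 + 2 + 1 = 23 in seven groups. DTI metrics are counted once, although the protocol plans both global and tract-specific values, so the real list is probably longer.

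**The plan's own figure.** The protocol states no error rate for this analysis. Its only related figure is power for the secondary outcome: effect size 0.60, 45 per group, 80%. Check: Φ(0.60/√(2/45) − 1.96) = Φ(2.846 − 1.96) = Φ(0.886) = 81% (80.4% with the noncentral t). It reproduces, so the sample size is sound, but it says nothing about predictor selection.

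**Closed form, independent candidates, no true effect.** The chance that at least one of k passes the screen is 1 − 0.95^k.

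- k = 7 (one per group): 1 − 0.95^7 = 30%.
- k = 14: 1 − 0.95^14 = 51%, the first count above one half.
- k = 23: 1 − 0.95^23 = 69%.

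**Simulation of the whole procedure.** Steps: screen at 0.05, best per group, forward stepwise at 0.05, overall F test. The outcome is pure noise, with 3,000 runs per setting, so the Monte Carlo standard error is at most √(0.25/3000) = 0.9 percentage points.

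| Correlation within / between modalities | Significant final model, n = 90 | n = 71 | Mean R-squared of those models, n = 90 | n = 71 |
|---|---|---|---|---|
| 0 / 0 | 69% | 69% | 0.085 | 0.107 |
| 0.3 / 0.1 | 65% | 64% | 0.083 | 0.103 |
| 0.5 / 0.2 | 61% | 60% | 0.075 | 0.096 |
| 0.7 / 0.3 | 51% | 51% | 0.072 | 0.089 |
| 0.8 / 0.5 | 37% | 40% | 0.067 | 0.084 |

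The rate hardly depends on n. Every simulated model that passed the screen also had an overall F p-value below 0.05. The models held on average 1.0 to 1.3 predictors, and with one predictor the F test is the screening test over again. The final test therefore adds no independent evidence.

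For comparison, one predictor fixed in advance has an expected null R-squared of 1/(n − 1): 1/89 = 0.011 and 1/70 = 0.014.

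**Three outcomes.** If the procedure is run for each of the three domains (assumed correlated 0.5), at least one yields a significant model in 71–95% of trials over the same settings.

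**Effect of correcting the screen.** With Benjamini-Hochberg at 5% over the 23 candidates, the null rate for one outcome falls to 3–5% at n = 90 and n = 71. Bonferroni gives about the same.

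**The case against.** The imaging work is Exploratory Aim 3a in what the protocol calls a pilot trial. This regression comes after the hypothesis tests and does not touch the primary memory analysis. Silence on correction is not a statement that none will be used: brain structure and connectivity are also listed as secondary outcomes, for which Benjamini-Hochberg is planned. Power analysis promises to report every proposed analysis and to judge by the overall pattern. Imaging measures are also correlated: mean diffusivity, for instance, is an arithmetic combination of axial and radial diffusivity. That lowers the rate.

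Much of this stands. The accurate criticism is that no multiplicity control is assigned to the screen, not that the plan rules one out. The rate depends on candidate count and correlation, and the screen drives it; the two later steps add to the bias in coefficients and R-squared rather than to the rate. But an exploratory label does not make an uncorrected p-value or an unvalidated R-squared interpretable, and adjusting across secondary outcomes is not the same as adjusting across candidate predictors.

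A reader might infer more than the documents support:

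- **Near-certain false positives.** Assuming 5, 10 or 20 independent features in each of six modalities gives 1 − 0.95^30 = 78.5%, 1 − 0.95^60 = 95.4% and 1 − 0.95^120 = 99.8%. The protocol gives no such counts, and independence is implausible.
- **Larger noise R-squared from a single arm of 45.** This paragraph does not say the regression is run within one arm. The within-group regressions in Exploratory Hypotheses concern inflammation and telomerase.
- **A worthless analysis.** Optimistic and unvalidated is the fair description.

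**Conclusion.** The concern holds in a conditional form. Followed as written, the procedure gives invalid p-values and an optimistic R-squared. For one outcome with no true predictor, a significant final model is expected in about 50–70% of trials at zero to fairly high correlation, about 40% at very high correlation, and 30% with one measure per modality, against a nominal 5%. Mean R-squared is about 0.07–0.11 with 71–90 women. These figures rest on my count of 23 candidates, a 0.05 screen and forward entry at 0.05, none of which the protocol fixes. That the documents leave these open is part of the problem. The paragraph should be changed, but it is a supporting analysis and the trial's primary conclusion does not depend on it.

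**What to change.** Rewrite the paragraph before imaging data are related to outcomes:

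1. List the candidate imaging measures, by modality, in advance.
2. Replace remission/relapse with change in the three domains that the section itself names. Mood should stay alongside memory and executive functioning.
3. Replace the screen and the stepwise step with one penalised regression, such as an elastic net. If the screen is kept, at least apply a 5% false discovery rate across all listed candidates. That alone controls false selection but leaves R-squared optimistic.
4. Repeat every selection and tuning step inside cross-validation, and report cross-validated R-squared with a permutation p-value.
5. Label the result hypothesis-generating.

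The cost is agreement on the candidate list and some programming, with no new visits, scans or participants. The downside is a smaller apparent predictive strength.

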Screening Procedures: Potential participants will receive a telephone screening. Only participants who are naïve to Kundalini Yoga and Kirtan Kriya or who have not practiced in the past year will be included in the study. Only participants currently not taking psychotropic medications prior to the initiation of the study will be enrolled. A research coordinator will assist with recruitment, screening, and scheduling.

A member of the research team will obtain informed consent from participants prior to the in-person screening. The in-person screening will include a questionnaire to collect demographic information, medications and medical and reproductive history. A physical exam and ECG for screening purposes will also take place at this time.

The baseline visit will include neuropsychiatric and physical examinations and laboratory tests. Though eligibility will be assessed at baseline, participation may be terminated if the subject stops meeting entry criteria. Dementia is an exclusion criterion. We will screen for possible incipient dementia and mild cognitive impairment of the amnestic subtype. This will include reviewing an extensive history and mental status exam together with corroborating information with regard to functional skills. A MMSE score of \leq 23 or an established dementia diagnosis will mandate exclusion. The evaluation for dementia includes: 1) an interview by a trained study staff to identify physical and cognitive limitations; 2) a standard battery of hematologic studies; 3) neuropsychological examination (detailed below); and 4) psychiatric evaluation as detailed above. Adjudication of dementia is based on DSM-5 criteria (Knopman et al., 2001; Lyketsos et al., 2002).

Inclusion criteria are:

1) Current subjective memory complaints:

- Frequency of at least once per week
- Able to provide an example of a recent memory difficulty
- Self-reported decline in memory ability since 5-10 years ago
- Self-reported concern about memory problems

2) High cardiovascular risk defined as at least one of the following:

- 7.5 percentile risk or higher using ASCVD risk calculator
- Myocardial Infarction more than 6 months ago
- Diabetes
- Taking medication for blood pressure
- \geq 140/90 blood pressure
- Taking medication for lyperlipidemia
- LDL≥160

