Autonomic nervous system (ANS) and respiratory measures. In order to link genotype and neuroimaging data with respiratory and ANS functioning, we will perform a series of five tests: 1) rest; 2) paced breathing; 3) breath hold; 4) Valsalva maneuver; 5) hand grip. These tasks will provide detailed information about cardiorespiratory functioning. Continuous blood pressure will be assessed using a probe attached to two fingers of the same hand. An additional finger probe will be used to measure the Galvanic skin response (GSR) and chest electrodes will be applied for the electrocardiogram (ECG) and on the hand for an electromyogram (EMG). A respiratory belt around the patient's chest will provide breath rate data and a small probe attached to the cheek will measure changes in face skin temperature. End-tidal CO2 will be measured using a capnometer and spirometry will be used to investigate pulmonary capacity. Verbal instructions will be provided and a computerized task will indicate to the subjects when to begin and end each challenge, for example when to prepare for the breath hold (deep inhale followed by deep exhale and then hold at the top of the next deep inhale). Data will be recorded and time-locked using a BioPac system and associated software, which will also be used to process the data.

Randomization and treatment schedule:

After all screening and baseline test results are reviewed and eligibility criteria are confirmed, patients will sign the informed consent form. Next, participants will be randomized to either MET or KK+KY groups using a computer-generated random assignment scheme, which assigns participants in a 1:1 ratio to each group using a customized module built into the centralized data system. All behavioral raters will be blind to the group assignment, and participants will be asked not to disclose their group assignment to the raters.

Study intervention procedures:

Participants will be randomized to: (1) MET class for 60 minutes per week plus daily homework; or (2) KY class for 60 minutes per week plus daily KK homework. Participants will complete a questionnaire about their treatment expectations after their second class. Follow-up assessments immediately after the intervention (12 weeks) as well as at 24 and 48 weeks will test the effect of the interventions at both short- and long-term follow-up.

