COVID-19 Questionnaire and Assessment. We will also instill a COVID-19 Questionnaire to all active participants to ensure optimal safety reporting and to correlate with current psychiatric measures. This will be administered as a survey, with the responses coming verbatim from the participant. We will also remotely administer HAMA and BDI at the same time point. This visit will only be administered once, but will happen as soon as possible once approved.

Compensation. Because the procedures are time-consuming, participants will receive a \$100.00 honorarium for their participation in the trial, which will be disbursed after completion of the 6-month follow-up assessment. Participants will receive an additional \$50 for completing the 12-month follow-up. Participants completing fMRI scans will receive \$50 per scan. Thus, the maximum amount a participant will be paid for her participation in the trial is \$250. In addition, we will offer reimbursement for parking up to \$234.00 for 18 visits, including classes.

All files will be kept in locked cabinets, as will copies of the signed informed consent forms to maintain the anonymity of participants and to bar any unauthorized access. The computerized database will be protected through the use of entry codes available only to authorized personnel.

In conjunction with the UCLA-NPI Human Subject Protection Committees (HSPC), as well as with the HSPC in all participating institutions, all legal and ethical safeguards for participants will be implemented. All participants will receive a copy of the Subject's Bill of Rights prior to giving consent to participate and will sign the Informed Consent form approved by the HSPC of UCLA-NPIH and affiliated institutions. They will receive a copy of the consent form.

Potential adverse effects of neuropsychological testing. Some study participants may experience mild frustration or boredom during testing. Clinicians administering neuropsychological tests are experienced in helping participants relax and feel comfortable during testing.

Discontinuation procedures. Discontinuation from the study will be considered if participants experience severe side-effects (rating of 3 or greater on the UKU Side Effect Rating scale). All severe adverse events will be reported to the participants, their psychiatrist and to their primary physicians and the UCLA IRB within one week of PI's awareness, and within two weeks to the funder.

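### The protocol gives two incompatible times for signing consent: before in-person screening, and after all screening and baseline results have been reviewed

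*Combined protocol and SAP*

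**What the plan says.** Two sections of the protocol fix the time of consent.

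Under Screening Procedures, candidates are first screened by telephone. Then: "A member of the research team will obtain informed consent from participants prior to the in-person screening". The in-person screening collects history and medications, and the section adds: "A physical exam and ECG for screening purposes will also take place at this time". The baseline visit comes after it: "The baseline visit will include neuropsychiatric and physical examinations and laboratory tests".

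Under Randomization and treatment schedule the order differs: "After all screening and baseline test results are reviewed and eligibility criteria are confirmed, patients will sign the informed consent form". The next sentence begins: "Next, participants will be randomized to either MET or KK+KY groups using a computer-generated random assignment scheme".

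Other sections say what belongs to baseline. The biomarker text says of blood sampling: "This will require 8 tablespoons of blood to be drawn at 3 time points (baseline, 12 weeks, and 6-month follow up". Imaging Biomarkers says: "Imaging data will be acquired from each subject at baseline and at 12- weeks postrandomization". Table 4 (assessment schedule) also places the neuropsychological battery, structural MRI, fMRI and the autonomic challenges in the Baseline column.

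Three further sections touch on consent without tying it to a visit. The human-subjects text after Compensation says "All participants will receive a copy of the Subject's Bill of Rights prior to giving consent to participate" and refers to one consent form. Retention of participants mentions consent as a continuing process. The Data and Safety Monitoring plan makes the principal investigator responsible for consent documentation.

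**The concern.** A coordinator working from Screening Procedures would have a signature before anyone was examined in person. A coordinator working from Randomization and treatment schedule could wait until every screening and baseline result was back. Both sections read as operating instructions, and the protocol does not say which governs.

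What is at stake is participant protection. The protocol itself lists risks for venipuncture, neuropsychological testing and MRI. The autonomic tests include a Valsalva manoeuvre, a breath hold and a hand grip task, in women selected for high cardiovascular risk. Capacity to consent is an inclusion criterion and screening may uncover dementia, so the time of consent should not be ambiguous in this population. The Data Sharing section also foresees passing study data to other researchers and to the sponsor. It should therefore be clear that screening and baseline data were collected under consent.

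**Working it through.** No test, power or sample size figure is involved. The check sets the two sequences side by side, places each procedure in them, and then bounds the number of women affected.

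**Step 1: the two sequences**

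| Order | Screening Procedures | Randomization and treatment schedule |
|---|---|---|
| 1 | Telephone screen | All screening and baseline tests |
| 2 | Consent | Results reviewed, eligibility confirmed |
| 3 | In-person screening, including examination and ECG | Consent form signed |
| 4 | Baseline visit | Randomisation |

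With a single consent event, step 2 of the left column and step 3 of the right cannot both be true.

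**Step 2: what falls before signature in the right-hand order**

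- Physical examination and screening ECG (Screening Procedures).
- Baseline laboratory tests (Screening Procedures) and the biomarker blood draw of 8 tablespoons (text following Inflammatory biomarkers).
- Neuropsychological battery (Table 4, Baseline column).
- Structural MRI and fMRI (Imaging Biomarkers; Table 4).
- Autonomic and respiratory tests (Autonomic nervous system and respiratory measures; Table 4).

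This takes baseline to mean before randomisation. Imaging Biomarkers supports that by contrasting baseline with 12 weeks after randomisation. One entry in the Baseline column of Table 4, treatment credibility, is marked week 2 and is left out.

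**Step 3: is there text that reconciles the two?** A separate screening consent and trial consent would do so. No section describes one, and the later section speaks of a single form with no hint of a second signature. The continuing-consent phrase under Retention of participants is listed as a retention strategy and sets no time. The consent pages are not in the text supplied, so the form itself cannot be checked.

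**Step 4: how many women**

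Inputs: about 250 screened and 100 recruited (Study Population). The protocol does not say whether the 250 are counted at the telephone or in person, nor how losses divide between the two.

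- Enrolled women: all 100, under the literal right-hand order.
- Screened but not enrolled: 250 − 100 = 150.
- Let T be the number of these who stop at the telephone screen. Then 150 − T attend in person without being enrolled.
- If T = 0: 150 − 0 = 150. If T = 150: 150 − 150 = 0.

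The range is therefore from near 0 to about 150. It applies to the in-person screening examination and ECG. A woman found ineligible there would normally not reach the baseline blood draw or MRI, so the number for those procedures is smaller again and cannot be derived from the documents.

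**Step 5: effect on the primary analysis.** In both orders every randomised woman has signed before randomisation. The Data analysis section specifies intention-to-treat for the primary analyses, and women who are never randomised do not enter them. The estimate, alpha, power and sample size are the same either way.

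**The case against.** The best defence is that the later sentence is loose wording. Screening Procedures is the dedicated text and orders the steps explicitly, while the other sentence is a lead-in to randomisation. The Recruitment section says participants are recruited, assessed and randomised under consent procedures approved by the review board. Both sentences could also be honoured if consent is given before screening and a form is signed again before randomisation.

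Most of this stands as a limit on the point. The earlier consent may well be the practice. A second signature is possible, so it would be too strong to say that only one sentence can be followed. The defence does not remove the contradiction, because the later sentence presents the signature as consent itself, not as a repetition, and nothing in the protocol tells staff otherwise.

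A reader might draw three stronger inferences that the documents do not support:

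- *That women are to be, or were, tested without consent.* The text contains a contradiction. It is not evidence of intent or conduct.
- *That about 150 women would undergo procedures without ever signing.* That is a ceiling. It assumes nobody fails by telephone, yet several criteria (yoga practice, psychotropic medication, recent surgery) can be asked by telephone. It also cannot describe the blood draw or MRI.
- *That the baseline values used in the primary analysis are compromised or unusable.* Everyone randomised has signed in either order, and no section states a rule on data collected before signature. A view on lawful use would be a legal conclusion from outside the documents.

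**Conclusion.** The point holds as an internal contradiction that should be corrected. Read literally, Randomization and treatment schedule places every in-person screening and baseline procedure before signed consent for all 100 enrolled women, and the in-person screening for between near 0 and about 150 others.

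This rests on three assumptions: there is one consent form, as the protocol's wording suggests; baseline tests means the pre-randomisation assessments in Table 4; and the 250 and 100 are the planned figures.

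The consequence is for participant protection and for the clarity of the operating instructions. It is not statistical: no primary estimate changes. The documents leave open that the order in Screening Procedures is what is actually followed.

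**What to change.** Reconcile the two sections in one of two ways:

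- delete the consent sentence from Randomization and treatment schedule, so that the section starts from confirmed eligibility and goes straight to randomisation; or
- recast it as reconfirmation, before randomisation, of the consent already given under Screening Procedures. If a second signature is intended, say so and name both forms.

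Either way the text should make clear that signed consent precedes every in-person screening and baseline procedure. It should not say every study procedure without qualification, because the protocol deliberately puts the telephone screen before consent and such wording would create a new conflict.

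The cost is one sentence in an amendment. No procedure, sample size or analysis changes.
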